### 2.2 RATIONALE

A new emerging technology in the area of aesthetic medicals device is LED (light-emitting diode) photo-modulation. It is currently being used to stimulate fibroblasts to produce collagen and to destroy bacteria on the skin. In this study, a 950 nm LED investigational device is being evaluated to determine if it is able to target adipocytes by maintaining a controlled temperature of 42-47 °C, similar to the reference device. In addition, the safety of the LED device will be compared to the reference device.

The use of this LED device has been determined to present non-significant risk for the intended use in this study, because the device is not:

- Intended as an implant and presents a potential for serious risk to the health, safety, or welfare of a subject;
- Is purported or represented to be for use supporting or sustaining human life and presents a potential for serious risk to the health, safety, or welfare of a subject;
- Is for a use of substantial importance in diagnosing, curing, mitigating, or treating disease, or otherwise preventing impairment of human health and presents a potential for serious risk to the health, safety, or welfare of a subject; or
- Otherwise presents a potential for serious risk to the health, safety, or welfare of a subject.

This study will be conducted in compliance with the protocol and according to Good Clinical Practice standards.

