#### 4.2.1 PRIMARY ENDPOINTS

Tissue temperature profiles compared to the reference device.

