#### **Treatment**

Based on the mild nature of treatment, anesthesia is not required. Treatment procedure should include positioning of the patient in a manner that enables access to the target treatment anatomical site. A water-based spray should be applied to the treatment area immediately prior to treatment.

Each subject will receive two consecutive treatments in the following order: the left flank of the abdomen will be treated with the diode laser device and the right flank of the abdomen will be treated with the LED device. The exact placement on the flank will be left to the principal investigator's judgement based on his assessment of individual subject requirements for treatment. Subjects will be treated on the same bilateral location with each device to ensure consistency of measurements. Both laser and LED applicators will be set to same output power level. Two levels will be used 41W (1.17W/cm^2) and 29W (0.83W/cm^2). The first level of 41W corresponds to initial heating for 4 minutes and the second level corresponds to duty cycle of 25 sec on and 10 sec off time. Total treatment time with each device will be 24 minutes (first 4 min at full power and next 16 min at duty cycle 25/10). Both device applicators have same output window dimensions and area 7x5 cm (35 cm^2). Both applicators are cooled by water chiller and therefore provided the same surface cooling temperature on skin.

Immediately (within 2 minutes) after treatment, 3 sterile thermocouple needles of different lengths (7-15 mm), will be inserted into the center of each applicator footprint. Temperature readings from each thermocouple needle will be recorded.

During treatment, subject reaction must be monitored and if the subjects verbally report an intolerable level of pain, treatment shall be ceased immediately.

The normal response to these treatments is transient erythema and edema. If any side effects occur other than a normal transient response, as indicated in the protocol, they will be recorded.

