#### **Post Treatment**

For post-treatment cooling, cold packs can be applied to treatment sites with protective gauze barrier immediately following cessation of treatment for up to 10 minutes, repeating as needed with rest periods of 5 minutes between applications. On the night following treatment, subjects should generally avoid hot water, cleanse their skin gently with tepid water, and hydrate the skin with a suitable moisturizer.

Subjects should be aware that post treatment erythema, edema and some discomfort of the treated areas are possible and should not be a cause for concern. Subjects may use NSAIDs to treat their pain. They may also experience some purpura in the treated areas which would be expected to resolve within several days.

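### Laser is always left and first and LED always right and second, so side and order are aliased with device in the primary temperature comparison; separately, the time of the temperature reading is not set

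*Combined protocol and SAP*

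**What the plan says.** The primary endpoint (protocol section 4.2.1) is "Tissue temperature profiles compared to the reference device". Section 10.3 analyses it by averaging the readings per device and per thermocouple and taking differences. It has no term for side, order or delay, and it plans no measure of spread or interval. Section 10.4 allows up to 10 subjects without a sample size calculation.

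Section 7.3.2 (Treatment) prescribes, for everyone enrolled, "two consecutive treatments in the following order: the left flank of the abdomen will be treated with the diode laser device". The LED session is listed next, with its side fixed as well: "the right flank of the abdomen will be treated with the LED device". Nothing in the document randomises or alternates this.

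On measurement, the same section says "Immediately (within 2 minutes) after treatment, 3 sterile thermocouple needles of different lengths (7-15 mm), will be inserted", and then only "Temperature readings from each thermocouple needle will be recorded". Under Post Treatment, "cold packs can be applied to treatment sites with protective gauze barrier immediately following cessation of treatment", with no statement that this comes after the reading. Under Assessment, the pain VAS is tied to within 5 minutes of a treatment and before the next one begins. The temperature reading has no such wording.

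Section 2.2 says the LED is being evaluated "to determine if it is able to target adipocytes by maintaining a controlled temperature of 42-47" °C. The only tissue readings described are taken after treatment.

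**The concern.** Each subject serves as his or her own control, which is a sound design for 10 people. It isolates the device only if nothing else differs systematically between the two flanks. Here two things always do: which flank, and which session. Any side effect (for example in fat thickness or applicator fit) or order effect (for example operator routine, or the subject's state after one heating session) would be reported as a device difference on the only primary endpoint. These mechanisms are only examples; the documents give no evidence for or against them.

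The reading time is a second and different problem. Tissue cools once power is off, so the temperature recorded depends on how long after power-off it is read and on whether the site has been cooled. The plan limits when the needles go in, but not when they are read, and no times are logged. A difference between flanks in delay or cooling would enter the endpoint unseen.

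**Working it through.** The plan contains no power or precision figure to reproduce. Three checks were made.

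**1. Aliasing (no assumptions needed).** Let D, S and O be the effects of LED versus laser, right versus left, and second versus first. Under section 7.3.2 every subject's LED-minus-laser difference has expectation D + S + O. The three columns of the design for the differences are identical, so its rank is 1 out of 3. Only the sum can be estimated, and more subjects do not change that.

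Now keep left-then-right but let the LED treat the left flank in half the subjects:
- Sequence A (laser left first, LED right second): expectation D + (S + O).
- Sequence B (LED left first, laser right second): expectation D − (S + O).

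The average of the two sequence means is D, and half their difference is S + O. Device is separated from the combined side/order effect, though S and O are not separated from each other. Swapping sides while always giving the laser first would not be enough, because order would stay aliased with device.

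**2. Precision cost.** The 95% half-width, in units of the SD of the within-subject differences, is t(0.975, n − 1)/√n with the fixed allocation. With an even split and sequence adjustment it is t(0.975, n − 2)/√n, assuming the same SD.

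| n | fixed | split, adjusted | ratio |
|---|---|---|---|
| 10 | 2.262/√10 = 0.715 | 2.306/√10 = 0.729 | 1.02 |
| 8 | 2.365/√8 = 0.836 | 2.447/√8 = 0.865 | 1.03 |
| 6 | 2.571/√6 = 1.049 | 2.776/√6 = 1.133 | 1.08 |

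A 6/4 split at n = 10 gives 2.306 × √[¼(1/6 + 1/4)] = 0.744.

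**3. Delay (illustration only).** The documents give no cooling rate, temperature rise or SD. Assume exponential cooling with one time constant τ for all depths, τ = 3, 5, 10 or 15 min, and a rise ΔT of 5 or 10 °C at power-off. The loss after t minutes is L(t) = ΔT(1 − e^(−t/τ)).

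*Each flank read after its own session.* If one flank is always read at 1 min and the other at 2 min, the spurious difference is L(2) − L(1):
- ΔT = 10 °C: 2.03, 1.48, 0.86, 0.60 °C for the four values of τ.
- ΔT = 5 °C: 1.02, 0.74, 0.43, 0.30 °C.

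At matched elapsed time it is zero. If instead the delays are independent and uniform over 0 to 2 min on each flank, with readings taken on insertion, the expected bias is also zero. The mean of 10 differences then carries extra chance error with SD 0.16 to 0.63 °C (ΔT = 10 °C) or 0.08 to 0.31 °C (ΔT = 5 °C).

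*Both flanks read after the second session.* The laser flank has cooled longer by at least one LED session: 20 min by the itemised phases or 24 min by the stated total. If the LED flank is read at power-off, the spurious difference is L(20) to L(24). Its lowest value is 5 × (1 − e^(−20/15)) = 3.7 °C and its highest is 10 × (1 − e^(−24/3)) = 10.0 °C. If the LED flank is read at 2 min, each value is multiplied by e^(−2/τ), giving 2.6 to 7.4 °C. The sign is the same in every subject, so delay is then itself aliased with device.

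**The case against.** The strongest reply has four parts.

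- **Settings are matched.** Section 7.3.2 gives both devices the same output power, window area, surface cooling and bilateral location, and the endpoint is an instrument reading. This stands as far as it goes. It equalises the devices' settings but does not remove a side or order effect.
- **No side or order effect has been shown.** This stands fully. The finding is that such an effect could not be told from a device effect, not that one is present.
- **This is a feasibility study with no hypothesis test.** That excuses the missing sample size calculation. It does not excuse a confounded primary comparison that can be repaired without extra subjects.
- **The sensible reading is that each flank is measured after its own session.** The 2-minute insertion limit and the VAS wording both point that way, and both flanks would then have the same insertion window. This is the likelier reading, but the text does not exclude the other.

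A reader might infer that delay, like side and order, is inseparable from device at any sample size. The documents do not support that. If each flank is read after its own session, delay can vary from subject to subject, and logged times with a matched reading time remove it even under the fixed allocation. Nor do they support treating 0.3 to 2.0 °C as the expected bias: nothing in the plan suggests that one flank is consistently read later.

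**Conclusion.** The concern holds in two separate parts.

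**Side and order** are exactly aliased with device in the primary comparison. This follows from the allocation alone and holds at any sample size. The size and direction of any resulting bias are unknown.

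**The reading time is uncontrolled.** On the likelier reading of section 7.3.2, delay adds unrecorded noise and becomes bias only if the mismatch between flanks is systematic. On the reading that both flanks are measured at the end, delay is fully aliased with device and could amount to several degrees, against a target band 5 °C wide (42 to 47 °C). All the temperature figures rest on assumed exponential cooling and assumed rises and time constants.

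Two lesser points follow. Without an SD or interval, a reader cannot judge a difference from up to 10 subjects. And post-treatment readings cannot show that a temperature was maintained during exposure, which is how section 2.2 frames the question.

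The plan should be changed, but the defect concerns interpretation of the primary comparison. It is not a sample size error.

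**What to change.** 1. **Allocation.** In section 7.3.2, use a prespecified list that alternates which device treats the left flank (5/5 at n = 10), keeping left-then-right. In section 10.3, estimate the within-subject LED-minus-laser difference adjusted for sequence. The cost is an allocation list and an interval about 2% wider at n = 10, 3% at n = 8 and 8% at n = 6. If alternation is not possible, state in section 10.3 and in the report that the difference combines device, side and order.

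2. **Reading time.** In section 7.3.2, state that each flank is read after its own session and before the next starts. Log the power-off, insertion and reading times. Compare devices at one prespecified elapsed time after power-off, the same on both flanks and the earliest the sensor allows. Earliest matters because delay also shrinks a true device difference: in the model above, e^(−3/τ) = 37% to 82% of it remains at 3 min. The sponsor must reconcile the Treatment and Post Treatment text so that both flanks are read under the same cooling condition. A longer needle dwell could affect the 5-minute VAS, so take the VAS at the same point relative to the needles on both flanks.

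3. **Reporting.** In section 10.3, give the mean within-subject difference with SD and 95% CI at each depth. Limit the conclusion to temperature shortly after treatment.

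4. **Separate point.** Section 7.3.2 states "Total treatment time with each device will be 24 minutes (first 4 min at full power and next 16 min at duty cycle 25/10", but 4 + 16 = 20; section 6.1.2 also gives 24 minutes. The sponsor must reconcile these. The discrepancy applies to both devices and does not bear on the confounding.

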#### **Post Treatment**

For post-treatment cooling, cold packs can be applied to treatment sites with protective gauze barrier immediately following cessation of treatment for up to 10 minutes, repeating as needed with rest periods of 5 minutes between applications. On the night following treatment, subjects should generally avoid hot water, cleanse their skin gently with tepid water, and hydrate the skin with a suitable moisturizer.

Subjects should be aware that post treatment erythema, edema and some discomfort of the treated areas are possible and should not be a cause for concern. Subjects may use NSAIDs to treat their pain. They may also experience some purpura in the treated areas which would be expected to resolve within several days.

## **Assessment**

The assessment of discomfort/pain based on the subject's report will be documented immediately (within 5 minutes) after treatment and before any subsequent treatment using the 10 cm VAS.

The investigator will examine the treated area and report immediate and short term response (30 minutes post-treatment) (pain during treatment, hemorrhage, burn, erythema, edema, purpura) using a 5 point scale: 1=none; 2=trace; 3=moderate; 4=marked; 5=severe.

The normal response to these treatments is transient erythema and edema. If any other side effects occur, as indicated in the protocol, they must be recorded. Subjects will be discharged from the clinic.

---

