#### 4.2.2 SECONDARY ENDPOINTS

### Safety objectives

Subject's assessment of discomfort and pain as measured by a 10 cm visual analog scale (VAS).

Subjects experiencing a treatment-related adverse event (AE).

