### 8.2.3 EXPECTEDNESS

Expected adverse reactions are AEs that are common and known to occur for the study agent being studied. Expected adverse events in this study include pain, tenderness, purpura, persistent erythema, edema, burn, blistering, crusting, hyperpigmentation, hypopigmentation, scarring and potential for damage to hair follicles within the treatment area and subsequent loss of hair within the treatment area.

An AE or suspected adverse reaction is considered "unexpected" if it is not known to occur for the study agent being studied and at the specificity or severity that has been observed.

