### 10.3 DESCRIPTION OF STATISTICAL METHODS

#### 10.4.1 GENERAL APPROACH

This is an open-label, comparative feasibility study of an investigational LED device and a diode laser device for non-invasive lipolysis of the flanks.

Mean temperature reading from each device and each thermocouple will be calculated and temperature differences will be determined.

The safety analysis will be done by analyzing spontaneous reports of adverse events (AE), subjects' completed 10 cm discomfort/pain VAS and short term response reports by the principal investigator from his/her observation/examination of the treated area. Appropriate Medical Dictionary for Regulatory Activities (MedDRA) code will be used to describe all spontaneously reported or other study related adverse events.

Summaries of spontaneously reported or other study related adverse events will be presented as:

- Number (%) of subjects with any AE,
- Number (%) of subjects with any serious adverse events (SAE),
- Number (%) of subjects permanently withdrawn from treatment due to AE

Summaries of analysis of immediate and short term response reports by the principal investigator examination will be displayed on a bar or pie chart as;

- the overall frequency of subjects with each event (pain during treatment, hemorrhage, burn, erythema, edema, purpura)
- Frequency of subjects with specific severity/intensity for each event using a 5 points scale: 1=none; 2=trace; 3=moderate; 4=marked; 5=severe
- The overall percentage or proportion of subject observed with marked or severe intensity of any event will be calculated and compared to those with none, trace or moderate severity/intensity with the aid of a bar or pie chart.

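### The pain VAS is neither ordered against the thermocouple needles nor limited to device discomfort, and the protocol text does not separate puncture-site findings in the skin score

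*Combined protocol and SAP*

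**What the plan says.** - **Needles.** Section 7.3.2, Treatment: "Immediately (within 2 minutes) after treatment, 3 sterile thermocouple needles of different lengths (7-15 mm), will be inserted into the center of each applicator footprint". This is done on both flanks.
- **Subject's pain report.** Section 7.3.2, Assessment: the report "will be documented immediately (within 5 minutes) after treatment and before any subsequent treatment using the 10 cm VAS". The only event it is ordered against is the next treatment. Section 4.2.2 names the endpoint as the subject's "assessment of discomfort and pain as measured by a 10 cm visual analog scale (VAS"), with no source of pain and no recall period.
- **Investigator's score.** The investigator examines the treated area and is to "report immediate and short term response (30 minutes post-treatment) (pain during treatment, hemorrhage, burn, erythema, edema, purpura"), each on a 5-point scale.
- **Summary.** Section 10.4.1 plans "the overall frequency of subjects with each event (pain during treatment, hemorrhage, burn, erythema, edema, purpura"), then frequencies by severity, and then marked or severe findings against the rest. It mentions neither device nor puncture site.
- **Overlap with device responses.** Section 7.3.2, Post Treatment, on what subjects may notice: "They may also experience some purpura in the treated areas which would be expected to resolve within several days". Section 8.2.3: "Expected adverse events in this study include pain, tenderness, purpura, persistent erythema, edema, burn", among others.
- **Aim.** Section 2.2 states that "the safety of the LED device will be compared to the reference device".
- **Schedule.** Section 7.3.6 lists temperature, VAS and investigator response under the same visit, with no stated sequence.

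**The concern.** The temperature measurement is itself a painful, skin-breaking procedure, and it takes place inside the area and the time window in which device safety is assessed. Two measures can pick it up.

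The VAS, a named safety endpoint, may be marked with three needles already in the flank, and nothing in the protocol tells the subject to leave needle pain out. The 30-minute skin score covers an area that has just been punctured, and several of its items are things a puncture can also produce. If the source is not noted at the visit, the analysis cannot use it later. What is at stake is how the absolute tolerability of the LED device is read and, to a lesser degree, how it compares with the laser.

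**Working it through.** The plan states no power, error rate or computed sample size, so there is no figure to reproduce. The check sets the time windows side by side, counts the exposed items, and illustrates the effect on labelled assumptions. I read the 2-minute rule as running from the end of each flank's own treatment.

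**1. Order of VAS and needles.** Needles: minute 0 to 2. VAS: minute 0 to 5. The first window lies wholly inside the second, so either order complies. If the needles are in by minute 2, a VAS marked after minute 2 follows them: (5 − 2)/5 = 60% of the VAS window. As an illustration only, with independent uniform times, P(VAS after needles) = 1 − (mean needle time)/5 = 1 − 1/5 = 80%. The documents do not say how the times are distributed.

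**2. What the VAS asks.** The Assessment wording attaches each VAS to the treatment just given, hence to one flank and one device. It does not limit the rating to the exposure period. The investigator's pain item does so by its name, but that item is not the subject-reported endpoint.

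**3. Timing of the skin score.** Minute 30 is later than minute 2, so every 30-minute score follows the punctures if the 2-minute rule is kept. With the maximum of 10 subjects, that is 10 × 2 = 20 flank scores and 3 × 2 × 10 = 60 punctures. The immediate score may fall on either side of the needles.

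**4. Items exposed.** Six are scored. Pain during treatment is excluded by its wording, and burn is taken (an assumption) as not caused by a puncture. Hemorrhage, erythema, edema and purpura remain: 6 − 2 = 4 of 6. If the frequencies were reported by device, this would be 4 × 2 = 8 of 6 × 2 = 12.

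**5. Step size.** With 10 subjects, one subject whose only finding for an event is a needle mark adds 1/10 = 10 percentage points to that event's frequency. With 5 subjects it adds 1/5 = 20. The marked-or-severe summary changes only if a needle mark is scored 4 or 5.

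**6. Effect on a device difference.** For the VAS, if each flank reads device discomfort plus the same needle contribution, the contribution drops out of the difference but stays in both levels. For a yes/no event with true device rate p and an independent needle mark with probability q on each flank:

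observed rate = 1 − (1 − p)(1 − q), so observed difference = (1 − q) × true difference.

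With assumed true rates of 10% and 30% (difference 20 points):

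| q (assumed) | Observed rates | Observed difference | Expected flanks with a needle mark, of 10 per device |
|---|---|---|---|
| 10% | 19%, 37% | 18 points | 1 |
| 30% | 37%, 51% | 14 points | 3 |
| 50% | 55%, 65% | 10 points | 5 |
| 80% | 82%, 86% | 4 points | 8 |

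The documents give no value for q and no needle-pain level, so these rows show the direction of the effect and do not estimate it.

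**The case against.** The strongest reply is that both flanks get the same three needles, so the effect cancels. For the VAS difference this largely stands, provided the order of VAS and needles is the same on both flanks, and nothing in the protocol requires that. The laser is always used on the left and first, and the LED on the right and second, so a change of order between flanks would coincide with device. Cancellation does not protect the absolute VAS levels, and step 6 shows that yes/no events are diluted rather than balanced out.

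Second, the forms are not in the documents. The VAS sheet may already ask about the device alone, and the skin-score CRF may already have a puncture entry. This stands: the point is about the protocol text only.

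Third, adverse events have their own route. Section 8.3 asks for an event description, and section 8.2.2 allows an event to be called not related once another cause is established. That limits the effect on the treatment-related adverse event endpoint, but it does not reach the 5-point score or the VAS.

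Fourth, this is an open-label feasibility study of at most 10 subjects with no safety test or margin. That argues for low severity, which I accept.

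Stronger readings are tempting, but the documents do not support them:
- A reader might infer that the VAS is not tied to a device at all. The Assessment wording does tie it to one.
- A reader might count 8 of 12 device-specific frequencies as affected. Section 10.4.1 plans overall subject frequencies; a split by device is only implied by the aim in section 2.2.
- A reader might conclude that a needle bruise can never be told from a device effect. The needles go into the center of a 35 cm² area that the investigator examines directly, and whether the marks can be distinguished is a clinical question the documents do not settle. What they show is that no protocol passage asks for the distinction to be recorded.

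**Conclusion.** The point holds for the protocol text, as something to consider and not as a flaw that invalidates the study. As written, needle pain can enter the VAS, and puncture-site findings can enter 4 of the 6 event frequencies in section 10.4.1 (8 of 12 only if they are reported by device). Absolute levels can be raised. A VAS difference between devices is largely protected if the order is the same on both flanks; a difference in yes/no events can be diluted. No bias in favor of one device is shown.

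The conclusion assumes that the 2-minute rule is kept on each flank, that burn is not a puncture effect, and that the unseen CRFs do not already resolve the matter. The size of the effect cannot be estimated from the documents.

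**What to change.** 1. **Section 7.3.2, Assessment.** State that the VAS rates discomfort during the device exposure only. Set in advance one order of VAS and needles, used on both flanks of every subject: VAS first if the sponsor confirms before the study that it fits the 2-minute needle window, otherwise needles first throughout. The order should not be decided flank by flank. Record both times.
2. **Skin-score CRF.** Record puncture-site hemorrhage, purpura, erythema and edema separately, at 30 minutes and also in the immediate score if that is taken after the needles. The immediate score need not be moved ahead of the needles.
3. **Section 10.4.1.** Summarise the events by device, with and without puncture-site findings, and remove nothing from the safety tables. The split by device is an addition to the current text.

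**Cost.** A few seconds before needle insertion if the VAS comes first, a few more CRF fields at up to two times, and extra summary rows. Treatment, visits and sample size do not change.
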